10.2.1. Adverse Events of Special Interest

TEAEs of special interest will be summarized by treatment group and pooled JZP150 treatment groups and may include the terms or categories noted below.

- Altered consciousness, such as somnolence and coma
- Cerebellar syndrome, such as limb ataxia, gait ataxia, postural ataxia, dysarthria, and nystagmus
- Other neurological symptoms, such as headache, dizziness, gait disturbance, slurred speech, blurred vision, amnesia

The listing of PTs of special interest will be reviewed and finalized prior to each database extraction for analysis specified in Section 10.2.

10.3. Laboratory Assessments

The continuous clinical laboratory assessments (hematology, chemistry, urinalysis, [REDACTED]
 [REDACTED]) will be summarized in Safety Analysis Set using descriptive statistics by treatment group and pooled JZP150 treatment groups by scheduled visit.

Change from baseline to each post-baseline visit for clinical laboratory values is (value at the post-baseline visit) – (baseline value). If the laboratory value is missing at either baseline or a specific post-baseline assessment for a participant, change between baseline and that assessment is unknown.

Values for any of the clinical laboratory values parameters that are below or above the limit of quantification of the assay (BLQ or ALQ), will be summarized using the BLQ or ALQ threshold value; the actual reported value will be listed.

Shift tables will summarize changes in clinical laboratory results by scheduled visit with respect to the Baseline result. Laboratory values are categorized into L1, low, normal, high, or H1 based on the laboratory reference range. L1 and H1 values are predefined per the laboratory vendor alert ranges and correspond to the extreme abnormal lower and higher ranges, respectively.

Abnormal laboratory assessments deemed clinically significant by the investigator will be reported as an AE.

A listing of participants with abnormal value(s) according to the following criteria will be provided using the Safety Analysis Set:

- Any laboratory value that falls into the pre-defined low or high panic ranges (L1 or H1) per the ICON laboratory panic value chart.
- Alanine aminotransferase (ALT) or aspartate aminotransferase (AST) $\geq 3 \times$ Upper Limit of Normal (ULN) and total bilirubin $> 2 \times$ ULN
- AST or ALT $\geq 5 \times$ ULN,
- Creatinine $\geq 176 \text{ } \mu\text{mol/L}$
- Participants positive for alcohol, urine drug screen or pregnancy assessments

Jazz Pharmaceuticals
 {Statistical Analysis Plan - Protocol #}JZP150-201-02

All laboratory results, including pregnancy test, drug screen, and alcohol screen, will also be presented in participant data listings.

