Abbreviations. AE = adverse event; AEA = anandamide; B-IPF = Brief Inventory of Psychosocial Functioning; E/D = Early Discontinuation; CAPS-5 = Clinician Administered PTSD Scale version 5; CGI-C = Clinical Global Impression of Change; CGI-S = Clinical Global Impression of Severity; C-SSRS = Columbia Suicide Severity Rating Scale; ECG = electrocardiogram; E/D = Early Discontinuation; [REDACTED] HbA1c = glycosylated hemoglobin; ISI = Insomnia Severity Index; LEC = Life Events Checklist; [REDACTED] MINI = Mini International Neuropsychiatric Interview; PCL-5 = Posttraumatic Checklist-5; PGI-S = Patient Global Impression of Severity; PHQ-9 = Patient Heath Questionnaire-9; PK = pharmacokinetics; PSQI-A = Pittsburgh Sleep Quality Index with PTSD Addendum; PTSD = posttraumatic stress disorder; ReQoL = Recovering Quality of Life; SAE = serious adverse event; SDS = Sheehan Disability Scale; SIGH-A = Structured Interview Guide for the Hamilton Anxiety Rating Scale; TSH = thyroid stimulating hormone; WOCBP= women of childbearing potential.

^a The E/D visit is conducted for participants who prematurely discontinue from the study intervention and the study.

- ^b The efficacy follow-up visit is conducted for participants who discontinue study intervention but remain in the study to complete scheduled assessments. For participants who discontinue study intervention early, every effort should be made to obtain an efficacy follow-up 12 weeks after first dose. An additional efficacy follow-up at 4 weeks is encouraged for participants who discontinue study intervention prior to Week 4. For those participants who discontinue study intervention but who otherwise continue in the study, the assessments included in these visits may be performed during the participants' safety follow-up visit if that efficacy follow-up is scheduled to occur within 2 after last dose of study intervention. This is meant to limit participant burden.
- ^c Participants will be instructed to start taking study intervention the day following their Baseline visit, which will be Day 1. Study intervention will be taken in the morning without regard for food.
- ^d Participants are required to fast for safety laboratory tests at the Baseline Visit (Visit 2), Week 1 (Visit 3), Week 4 (Visit 5), Week 12 (Visit 9), Early Discontinuation (Visit 10), if applicable, and Safety follow-up Visit (Visit 12). Participants are not required to fast for laboratory tests at the Screening Visit or Week 8 (Visit 7).

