8. STUDY ASSESSMENTS AND PROCEDURES

Efficacy, safety, PK/PD sampling will be collected during clinic visits as outlined in the SoA. In addition, telephone calls will be conducted between clinic visits in order to (1) assess safety and (2) maintain engagement with the participants to mitigate attrition rates which are high in this patient population.

Study procedures and their timing are summarized in the SoA ([Section 1.3](#)).

For clinic visits, participants should check-in to the study site in the morning, with the exception of the Week 8 visit, which should be scheduled for the afternoon/ evening. Participants should dose at home in the morning on the day of the Week 8 clinic visit. The investigator may opt to have the participant attend an unscheduled visit, if deemed necessary, at any time during the study. Some clinic visits may be shortened and/or conducted remotely, if required due to the COVID-19 (or other) pandemic, and with approval from the Sponsor's Medical Monitor, as noted in the SoA ([Section 1.3](#)). Protocol waivers or exemptions are not allowed.

All screening evaluations must be completed by the principal investigator (PI) or sub-investigator and reviewed to confirm that potential participants meet all eligibility criteria. The investigator should maintain a screening log to record details of all participants screened and to confirm eligibility or record reasons for screening failure, as applicable.

After screening procedures have been completed and eligibility criteria have been confirmed, eligible participants will be provided with instructions on how to discontinue any excluded medications. It should be documented that the investigator has determined that discontinuation is safe and medically appropriate, and the discontinuation is medically supervised. The medical monitor should be contacted if there are any questions regarding discontinuation of excluded medications.

For clinical outcome assessment measures that are rated by specially qualified and trained interviewers/raters, the same person should perform each assessment for the same participant throughout the duration of the study, whenever possible.

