APPENDIX 3. CLINICAL LABORATORY TESTS

The tests detailed in [Table 6](#) will be performed by the central laboratory, with the exception of urine pregnancy, urine dipstick for drug screen (with the exception of the screening visit during which urine drug screen will be done by the central lab), and breath alcohol tests, which will be performed locally.

Participants are required to fast for safety laboratory tests at the Baseline Visit (Visit 2), Week 1 (Visit 3), Week 4 (Visit 5), Week 12 (Visit 9), Early Discontinuation (Visit 10), if applicable, and Safety Follow-up Visit (Visit 12). Participants are not required to fast for laboratory tests at the Screening Visit or Week 8 (Visit 7).

Local laboratory results are only required in the event that the central laboratory results are not available in time for either study intervention administration and/or response evaluation. If a local sample is required, it is important that the sample for central analysis is obtained at the same time. Additionally, if the local laboratory results are used to make either a study intervention decision or response evaluation, the results must be recorded.

Protocol-specific requirements for inclusion or exclusion of participants are detailed in [Section 5](#) of the protocol.

Additional tests may be performed at any time during the study as determined necessary by the investigator or required by local regulations.

Investigators must document their review of each laboratory report.

Table 6: Protocol-Required Safety Laboratory Tests

Laboratory Tests	Parameters				
Hematology ^a	Platelet Count	RBC Indices: MCV MCH Reticulocytes (count, absolute)	WBC count with Differential: Neutrophils Lymphocytes Monocytes Eosinophils Basophils		
	RBC Count				
	Hemoglobin				
	Hematocrit				
Clinical Chemistry ^{ab}	Albumin	ALP ^c	ALT/ SGPT	AST/ SGOT	
	BUN	Calcium	CO ₂	Chloride	
	Creatinine	Creatine kinase	GGT	Glucose	
				HbA1c (Screening and Week 12 only)	
	Lactate dehydrogenase	Phosphorus	Potassium	Sodium	
	TSH (Screening only)	Total and direct bilirubin	Total cholesterol	Total protein	

Laboratory Tests	Parameters			
	Triglycerides	Uric acid	High-density lipoprotein cholesterol	Low-density lipoprotein cholesterol
	LH (males only)	FSH (collected at Screening only for WONCBP when needed; collected at [REDACTED])	Serum testosterone (males only)	

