7.2. Baseline and Study Day Definitions

7.2.1. Baseline

For the study assessments that are either clinician-reported or patient-reported outcomes (CAPS-5, CGI-S, CGI-C, PGI-S, PCL-5, B-IPF, ReQoL-10, SDS, PSQI, PSQI-A, ISI, PHQ-9, SIGH-A, MWC, and C-SSRS), the baseline value is defined as the initial value obtained on the date of the Baseline Visit (Day -1). If this value is missing, the last non-missing value obtained prior to the first dose of study intervention will be used as the baseline value. Repeat assessments performed on the same Baseline Visit date will be included in the clinical database as unscheduled assessment but will not be utilized for analyses. If the scheduled Baseline Visit occurred on the same day (Day 1) of first dosing, the assessment of the above-mentioned endpoints should be considered prior to first dosing.

For all other assessments, the last non-missing value obtained prior to the initiation of study intervention will be used as the baseline value.

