APPENDIX 3: ICON LABORATORY SERVICES (ILS) STANDARD ADULT PANIC VALUES

TEST	Conventional Units	Reference Interval	Panic Value < or =	Panic Value > or =	SI Units	Reference Interval	Panic Value < or =	Panic Value > or =
Glucose, Fasting Serum/Plasma	mg/dL	74-99	40 (F) 50 (M)	400	mmol/L	4.10-5.50	2.20 (F) 2.80 (M)	22.20
Glucose, Random Serum	mg/dL	74-139	40 (F) 50 (M)	400	mmol/L	4.10-7.74	2.20 (F) 2.80 (M)	22.20
Calcium	mg/dL	8.4-10.2 (F, >= 18 yrs); 8.4-10.2 (M, 18 yrs to <61 yrs); 8.8-10.0 (M, >=61 yrs)	6.0	14.0	mmol/L	2.10-2.55 (F, >= 18 yrs); 2.10-2.55 (M, 18 yrs to <61 yrs); 2.20-2.50 (M, >=61 yrs)	1.50	3.50
Adjusted Calcium	mg/dL	8.4-10.2 (F, >= 18 yrs); 8.4-10.2 (M, 18 yrs to <61 yrs); 8.8-10.0 (M, >=61 yrs)	6.0	14.0	mmol/L	2.10-2.55 (F, >= 18 yrs); 2.10-2.55 (M, 18 yrs to <61 yrs); 2.20-2.50 (M, >=61 yrs)	1.50	3.50
Potassium	mmol/L	3.5-5.1	2.5	6.5	mmol/L	3.5-5.1	2.5	6.5
Total Bilirubin	mg/dL	Less than or = 1.20	-	3.33	μmol/L	Less than or = 20.5	-	57.0

Jazz Pharmaceuticals
 {Statistical Analysis Plan - Protocol #}JZP150-201-02

CK	U/L	29-168 (F) 30-200 (M)	-	850 (F) 975 (M)	U/L	29-168 (F) 30-200 (M)	-	850 (F) 975 (M)
Platelets	$\times 10^9/L$	15-400	50	1000	$\times 10^9/L$	15-400	50	1000
Platelets, Na Citrate	$\times 10^9/L$	131-362	39	914	$\times 10^9/L$	131-362	39	914
WBC	$\times 10^9/L$	3.50-11.10	2.50	30.00	$\times 10^9/L$	3.50-11.10	2.50	30.00
HGB	g/dL	11.5-15.5 (F) 13.2-17.0 (M)	8.0	18.0	g/dL	11.5-15.5 (F) 13.2-17.0 (M)	8.0	18.0
PT	Sec	11.8-14.7	-	25.0	Sec	11.8-14.7	-	25.0
APTT	Sec	20.4-35.1	-	70.0	Sec	20.4-35.1	-	70.0
INR	Ratio	0.8-1.1	-	5.0	Ratio	0.8-1.1	-	5.0
HCG, Quantitative	mIU/mL	Less than or = 5.00 (F) No Reference Range (M)	-	5.01 (F)	IU/L	Less than or = 5.00 (F) No Reference Range (M)	-	5.01 (F)

Jazz Pharmaceuticals
 {Statistical Analysis Plan - Protocol #}JZP150-201-02

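### SAP 10.3 compares Week 8 laboratory values, which need not be fasting, with a normally fasting Baseline, so within-arm Week 8 changes in glucose and lipids can reflect meals.

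*SAP*

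**What the plan says.** **Fasting.** Footnote d to the schedule in Protocol 1.3, repeated in Protocol Appendix 3, states: "Participants are required to fast for safety laboratory tests at the Baseline Visit (Visit 2"; the same list covers Weeks 1, 4 and 12, Early Discontinuation and Safety Follow-up. It then states: "Participants are not required to fast for laboratory tests at the Screening Visit or Week 8 (Visit 7".

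**Time of day.** Protocol 8 has participants check in to clinic visits in the morning, "with the exception of the Week 8 visit, which should be scheduled for the afternoon/ evening".

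**Analytes.** The chemistry panel in Protocol Appendix 3 includes glucose, "Triglycerides", and total, HDL and LDL cholesterol.

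**Analysis.** SAP 10.3 gives one rule for all chemistry. "Change from baseline to each post-baseline visit for clinical laboratory values is" the visit value minus the baseline value, and "Shift tables will summarize changes in clinical laboratory results by scheduled visit with respect to the Baseline result". There is no exception or footnote for fasting status, and SAP 7.7, which lists departures from the protocol, does not mention it.

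**Baseline.** Under SAP 7.2.1, for laboratory data, "the last non-missing value obtained prior to the initiation of study intervention will be used as the baseline value".

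**Reference ranges.** SAP 10.3.1 classifies each result against whichever laboratory range is relevant. SAP Appendix 3 lists fasting glucose and "Glucose, Random Serum" as separate tests.

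**The concern.** A change from baseline is interpretable when both samples are taken under comparable conditions. Here the Baseline sample is normally fasting and taken in the morning, while the Week 8 sample may follow meals. For analytes that respond to food, the within-arm Week 8 change adds any meal effect to any drug effect, and the table as specified would not show that.

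The baseline rule can produce the reverse mismatch. If the fasting Baseline value is missing, a Screening value that need not be fasting takes its place, and the fasting visits are then compared with it.

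What is at stake is the reading of descriptive safety tables. A movement at Week 8 that is absent at Week 12 would need explaining, and a reader of the within-arm tables could not tell meals from drug.

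**Working it through.** The plan states no figure that can be reproduced on this point. The check sets the rules side by side and then adds an illustration on assumed values.

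**1. Conditions by visit** (Protocol 1.3 and 8; laboratory visits from SAP Table 3)

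| Visit | Fasting required | Time of day |
|---|---|---|
| Screening | No | Morning |
| Baseline | Yes | Morning |
| Weeks 1, 4, 12 | Yes | Morning |
| Week 8 | No | Afternoon or evening |

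One of the four scheduled on-treatment laboratory visits differs from Baseline in both respects.

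**2. The Week 8 cell can be mixed.** The laboratory window for Week 8 in SAP Table 3 is Days 43 to 70, and SAP 7.2.3 admits unscheduled and early-termination samples. Early Discontinuation samples are fasting. Selection within the window goes by closeness to the scheduled day, not by fasting status.

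**3. Glucose ranges** (SAP Appendix 3)

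- Fasting: 74–99 mg/dL (4.10–5.50 mmol/L)
- Random: 74–139 mg/dL (4.10–7.74 mmol/L)
- Difference in upper limits: 139 − 99 = 40 mg/dL; 7.74 − 5.50 = 2.24 mmol/L
- The panic limits are the same for both tests, so the choice of range moves only the boundary between normal and high.

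The 40 mg/dL is a gap between two limits, not an expected change.

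**4. What the SAP leaves open for glucose**

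- One parameter, all samples on the fasting limit: normal-to-high shifts at Week 8 tend to increase.
- One parameter, non-fasting samples on the random limit: high-to-normal shifts tend to increase.
- Two parameters: the last pre-dose random value is the Screening value (SAP 7.2.1), or, if there is none, no change is computed (SAP 10.3).

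**5. Illustration on assumed values, none taken from the documents.** Fasting glucose is normal with mean 90 and SD 9 mg/dL. Non-fasting Week 8 glucose has mean 90 + d and SD 15. A share s of Week 8 samples is non-fasting. Then:

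- Mean change in each arm without any drug effect = d × s
- Percent high on the fasting limit = (1 − s) × P[N(90, 9) > 99] + s × P[N(90 + d, 15) > 99]
- Percent high with non-fasting samples on the random limit: the same, with 139 in place of 99 in the second term
- Percent high at Baseline = P[N(90, 9) > 99] = P(Z > 1) = 15.9%

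| d (mg/dL) | s | Mean change (mg/dL) | % high, limit 99 | % high, limit 139 for non-fasting |
|---|---|---|---|---|
| 0 | 0.5 | 0 | 21.6 | 8.0 |
| 0 | 1.0 | 0 | 27.4 | 0.1 |
| 5 | 0.5 | 2.5 | 27.7 | 8.0 |
| 5 | 1.0 | 5 | 39.5 | 0.2 |
| 10 | 0.5 | 5 | 34.3 | 8.2 |
| 10 | 1.0 | 10 | 52.7 | 0.5 |
| 20 | 0.5 | 10 | 46.3 | 9.3 |
| 20 | 1.0 | 20 | 76.8 | 2.7 |

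The rise at d = 0 comes from the wider assumed SD alone. Against 15.9% at Baseline, the proportion high goes up in every row on one limit and down in every row on the other. The mean change moves by d × s whichever limit is used.

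**6. Between arms.** If d × s is the same in each arm, it cancels: (drug change + d × s) − (placebo change + d × s) = drug change − placebo change.

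**7. Triglycerides.** SAP Appendix 3 has no triglyceride entry, so no separate non-fasting range is visible that could offset the effect on shifts.

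**The case against.** The strongest reply is that the trial is randomised, double-blind and placebo-controlled, and SAP 10.3 tabulates by treatment group. A meal effect common to all arms leaves the Week 8 comparison with placebo readable. Protocol 9.4.5 makes all safety analyses descriptive. Fasting samples remain at Weeks 1, 4 and 12, and HbA1c is measured at Screening and Week 12. For glucose, the laboratory already holds a random range, and SAP 10.3.1 may be meant to invoke it. A footnote might then be enough.

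Most of this stands, and it keeps the point minor. It does not repair the within-arm change and shift tables, which are planned outputs. The random range can help only the glucose category. It does nothing for mean change or for triglycerides, and HbA1c does not inform on lipids.

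A reader might infer more: that the tables will show a false Week 8 rise in every arm, and that no metabolic signal can be read at that visit. The documents do not support this. Not requiring a fast does not make every sample non-fasting, no food effect is given, glucose shifts could go either way, and the placebo contrast remains. The substitution of Screening for Baseline arises only when the scheduled value is missing, and no frequency is given.

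**Conclusion.** The gap is real and minor. As written, SAP 10.3 lets within-arm Week 8 mean changes in glucose, triglycerides and other fasting-dependent lipids, and triglyceride shifts, carry meal effects. It also leaves the direction of glucose shifts to an unstated choice between upper limits of 99 and 139 mg/dL.

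One of four on-treatment laboratory visits is affected. The size cannot be derived from the documents; the illustrative mean shift of 0 to 20 mg/dL rests wholly on assumed values. The expectation that the between-arm comparison is largely unaffected assumes similar food intake and a similar mix of fasting and non-fasting samples across arms. Efficacy results are not involved.

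SAP Appendix 4 was not in the text available for review. Its title concerns panic values only, but a study-specific rule there cannot be excluded.

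**What to change.** Add to SAP 10.3, for glucose, triglycerides and other fasting-dependent lipids:

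- Restrict change-from-baseline and shift tables to fasting samples with a fasting Baseline value, so that a non-fasting Screening value does not serve as Baseline for these analytes under SAP 7.2.1.
- Present Week 8 by treatment group as observed values, labelled non-fasting. This keeps the comparison with placebo visible.
- Judge non-fasting glucose on the random-glucose range in SAP Appendix 3.
- State how fasting status is determined, since the documents do not say whether it is recorded for each sample. If it is not, classify scheduled samples by visit and give a rule for unscheduled ones.

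The cost is a short addition to the SAP and a programming filter, with one fewer change time point for these analytes. Fasting change data remain at Weeks 1, 4 and 12.

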10.1.9.2. Study/Site Termination

The sponsor or designee reserves the right to close the study site or terminate the study at any time for any reason at the sole discretion of the sponsor. Study sites will be closed upon study completion. A study site is considered closed when all required documents and study supplies have been collected and a study site closure visit has been performed.

Administration of the study agent will be temporarily suspended by the SMT upon the occurrence of any of the following:

- Unexpected SAEs within the same SOC or similar in nature are reported by 2 or more participants on active study intervention with a plausible relationship to study intervention administration.
- 1 or more participants on active study intervention meets Hy's Law Criteria as defined in [Appendix 7](#).

Based on the sponsor review and evaluation of the aforementioned safety events, the study may be restarted or terminated.

The investigator may initiate study site closure at any time, provided there is reasonable cause and sufficient notice is given in advance of the intended termination.

Reasons for the early closure of a study site by the sponsor or investigator may include but are not limited to:

For study termination:

- Sponsor makes a business decision to stop the study.
- Study stopping criteria are met and following investigation, the sponsor decides to stop the study.
- Ongoing evaluation of study safety data suggests that the benefit-risk profile suggests stopping the study.

For site termination:

- Failure of the investigator to comply with the protocol, the requirements of the IRB/IEC or local health authorities, the sponsor's procedures, or GCP guidelines
- Inadequate or no recruitment (evaluated after a reasonable amount of time) of participants by the investigator
- Total number of participants included earlier than expected

If the study is prematurely terminated or suspended, the sponsor shall promptly inform the investigators, the IECs/IRBs, the regulatory authorities, and any contract research organization(s) used in the study of the reason for termination or suspension, as specified by the applicable regulatory requirements. The investigator shall promptly inform the participant and should assure appropriate participant therapy and/or follow-up.

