Routine Urinalysis	
 Appearance, color Specific gravity pH, glucose, protein, blood, ketones, bilirubin, urobilinogen, nitrite, leukocyte esterase (by dipstick) Microscopic examination (if blood or protein is abnormal) Urinalysis will always be conducted by the central laboratory. 			
Pregnancy testing	
 Highly sensitive serum or urine hCG pregnancy test (as needed for WOCBP)^d 			
Other Screening Tests	
 Follicle-stimulating hormone and estradiol (as needed for WONCBP) Urine drug screen (to include at minimum: amphetamines, barbiturates, cocaine, opiates, cannabinoids and benzodiazepines). Note: The urine drug screen will be conducted by the central laboratory at Screening and the urine drug screen at subsequent visits after screening will be conducted locally at the site. In the case of a positive urine drug screen at the site, samples can be sent to the central laboratory for confirmation. Breath alcohol test 			

Abbreviations: ALP = alkaline phosphatase; ALT = alanine aminotransferase; AST = aspartate aminotransferase; BUN = blood urea nitrogen; FSH = follicle-stimulating hormone; GGT = gamma-glutamyl transferase; HbA1c = glycosylated hemoglobin; hCG = human chorionic gonadotropin; LH = luteinizing hormone; MCH = mean corpuscular hemoglobin; MCV = mean corpuscular volume; MDMA = 3, 4,-methylenedioxymethamphetamine; RBC = red blood cell; SGOT = serum glutamic-oxaloacetic transaminase; SGPT = serum glutamic-pyruvic transaminase; TSH = thyroid stimulating hormone; WBC = white blood cell; WOCBP = woman of childbearing potential; WONCBP = woman of non-childbearing potential.

^a Participants are required to fast for safety laboratory tests at the Baseline Visit (Visit 2), Week 1 (Visit 3), Week 4 (Visit 5), Week 12 (Visit 9), Early Discontinuation (Visit 10), if applicable, and Safety follow-up Visit (Visit 12). Participants are not required to fast for laboratory tests at the Screening Visit or Week 8 (Visit 7).

^b All events of ALT (or AST) $\geq 3 \times$ upper limit of normal (ULN) and total bilirubin $\geq 2 \times$ ULN ($> 35\%$ direct bilirubin) or ALT (or AST) $\geq 3 \times$ ULN and international normalized ratio (INR) > 1.5 , (if INR measured) which may indicate severe liver injury (possible Hy's Law), must be reported to the sponsor or designee in an expedited manner.

^c If alkaline phosphatase is elevated, consider fractionating.

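### The combined liver criterion in the SAP 10.3 listing has no INR alternative and uses bilirubin strictly above 2 × ULN, so it does not match the protocol's possible Hy's Law definition (minor)

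*SAP*

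**What the plan says.** **SAP 10.3 (Laboratory Assessments)** plans a listing of participants with abnormal values. Three of its criteria can pick up a liver case:

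- ALT or AST at or above 3 × ULN "and total bilirubin $> 2 \times$ ULN";
- "AST or ALT $\geq 5 \times$ ULN" on its own;
- "Any laboratory value that falls into the pre-defined low or high panic ranges (L1 or H1) per the ICON laboratory panic value chart".

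The panic chart is in SAP Appendix 3. Its total bilirubin entries in µmol/L (reference limit, no low panic value, high panic value) read "Less than or = 20.5 - 57.0". The high panic value for INR is 5.0. SAP 10.3.1 also points to Appendix 4 for study-specific changes to these limits.

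**Protocol Appendix 3, Table 6 footnote b** describes possible Hy's Law as ALT (or AST) at or above 3 × ULN with one of two alternatives. The first is "and total bilirubin $\geq 2 \times$ ULN ($> 35\%$ direct bilirubin"). The second is "international normalized ratio (INR) > 1.5 , (if INR measured"). Such events "must be reported to the sponsor or designee in an expedited manner".

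**Protocol Appendix 7** (Table 7 and its footnote b) repeats both alternatives with ALT only. It adds that the INR threshold does not apply to participants on anticoagulants.

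**Protocol 10.1.9.2** has the Safety Management Team suspend dosing when "1 or more participants on active study intervention meets" the Hy's Law criteria of Appendix 7.

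**The concern.** In the SAP as provided, this listing is the only pre-specified output that puts transaminases and liver function together. The shift tables take one laboratory parameter at a time. The adverse events of special interest in SAP 10.2.1 name only neurological categories, although protocol 10.1.5 includes hepatic-related events among those its safety committee reviews.

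A reader of the study report will naturally use this listing to see whether any participant had a combined liver abnormality. If its criterion is narrower than the protocol's definition, it can show no such case although the definition was met. SAP 7.7, which sets out changes to the protocol's statistical section, does not mention the difference, and nothing else in the SAP explains it.

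**Working it through.** No figure in the plan needs reproducing. The check is whether the protocol definition is contained in the SAP listing rule.

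**Notation.** T = the higher of ALT and AST, B = total bilirubin (both as multiples of ULN), D = direct fraction of bilirubin, INR where measured.

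**Inputs**

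| Item | Value | Source |
|---|---|---|
| Protocol definition | T ≥ 3 and [(B ≥ 2 and D > 35%) or INR > 1.5] | Protocol Table 6 footnote b |
| SAP combined criterion | T ≥ 3 and B > 2 | SAP 10.3 |
| SAP transaminase criterion | T ≥ 5 | SAP 10.3 |
| Bilirubin ULN; high panic value | 20.5; 57.0 µmol/L | SAP Appendix 3 |
| INR high panic value | 5.0 | SAP Appendix 3 |

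**Step 1: panic limit on the ULN scale.** 57.0 / 20.5 = 2.78 × ULN. In conventional units, 3.33 / 1.20 = 2.775 × ULN. This lies above 2 × ULN, so for T ≥ 3 the bilirubin panic rule adds nothing to the combined criterion.

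**Step 2: the SAP rule.** A participant is listed on liver grounds if (T ≥ 3 and B > 2), or T ≥ 5, or B ≥ 2.78, or INR ≥ 5.0.

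**Step 3: protocol definition met, SAP rule not met.** Not being listed requires T < 5, B ≤ 2 and INR below 5.0 or not measured. Combined with the protocol definition, two regions remain:

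- (a) 3 ≤ T < 5, B ≤ 2, 1.5 < INR < 5.0;
- (b) 3 ≤ T < 5, B exactly 2.0 (2 × 20.5 = 41.0 µmol/L), D > 35%, INR not measured or below 5.0.

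**Step 4: examples**

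| T | B | D | INR | Protocol definition | Visible SAP rule |
|---|---|---|---|---|---|
| 4 | 1.0 | any | 1.6 | met | not met |
| 4 | 2.0 | 40% | not measured | met | not met |
| 4 | 2.05 | 40% | not measured | met | met |
| 5 | 1.0 | any | 1.6 | met | met (T ≥ 5) |
| 4 | 2.05 | 30% | not measured | not met | met |

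The first row is the substantive gap. The second exists only at a single value. The last shows the SAP is wider in one respect, since it sets no direct-fraction condition.

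**Step 5: can an INR exist in region (a)?** INR is not a routine Table 6 test, and the Table 8 weekly repeat panel for ALT from 3 to below 5 × ULN does not include it. The work-up after a liver stopping event (Table 7) does. Stopping events include ALT at or above 3 × ULN that persists for at least 4 weeks, or that comes with symptoms. Both can occur below 5 × ULN, so region (a) can be reached, though rarely.

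**Step 6: after alignment.** With the rule T ≥ 3 and (B ≥ 2 or INR > 1.5 where measured), every case meeting the Table 6 definition is listed. The missed set is empty by construction.

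**The case against.** The case for leaving the listing alone has several parts, and most of them stand as limits on the point.

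- **The panic chart is not fully visible.** SAP Appendix 4 may change the INR or bilirubin limits. This stands. A reader might infer that the case in region (a) meets no listing criterion at all, but the documents support that only for the Appendix 3 limits. A participant could also be listed for an unrelated panic value. The combined criterion would still differ from the protocol.
- **The information is not lost.** ALT at or above 3 × ULN with INR above 1.5 is a stopping criterion under Appendix 7. It must be recorded as an adverse event and sent to the sponsor as an other reportable experience, or as an SAE if it qualifies. SAP 10.2 lists all AEs, SAEs and AEs leading to permanent withdrawal, and SAP 10.3 lists all laboratory results. This stands: what is missing is the automatic flag.
- **Suspension does not run through this listing.** A reader might infer that a suspension-triggering case could be overlooked. The documents do not support that. The Safety Management Team acts during conduct, with ongoing safety review and expedited reports available, and nothing makes the SAP listing an input.
- **There are two protocol definitions.** Table 6 takes ALT or AST; Appendix 7, which the suspension rule cites, takes ALT only. It would be wrong to say that every Table 6 case triggers suspension: an AST-only case does not meet Appendix 7.
- **The SAP never calls this a Hy's Law listing,** and protocol 9.4.5 promises only descriptive laboratory summaries. This also stands, so no promised analysis is missing. SAP 7.7 covers changes to the statistical section, so its silence shows only that the difference is unexplained.

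None of this removes the mismatch. The SAP sets a combined liver criterion close to the protocol's and leaves out one of its two alternatives.

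**Conclusion.** The point holds as a minor inconsistency. The SAP 10.3 criterion does not contain the protocol's possible Hy's Law definition. The gap that matters is the INR alternative: transaminases from 3 to below 5 × ULN, bilirubin up to 2 × ULN and INR above 1.5 but below 5.0. The difference between strictly above and at or above is confined to a bilirubin of exactly 2 × ULN (41.0 µmol/L at the stated limit).

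The size rests on three conditions: the Appendix 3 panic limits apply unchanged, an INR was obtained, and the participant was not on an anticoagulant where Appendix 7 governs. The documents give no expected count. Because INR is obtained mainly in stopping-event work-ups, few cases are likely. The consequence is incomplete identification in the study report. It does not reach participant monitoring, expedited reporting or the suspension decision. No view is taken here on which clinical threshold is right; the two documents need to be reconciled.

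**What to change.** Reconcile the SAP 10.3 criterion with the protocol's own definition:

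1. List participants with ALT or AST at or above 3 × ULN together with either total bilirubin at or above 2 × ULN, or INR above 1.5 where measured.
2. Show the direct-bilirubin fraction and anticoagulant use as flags. The listing is then slightly wider than the protocol definition, and the reader can see which cases satisfy the more-than-35%-direct condition and which fall under the anticoagulant exception.
3. Mark which listed cases meet the ALT-only Appendix 7 definition, since that is the one 10.1.9.2 cites.
4. Check Appendix 4 for any study-specific INR or bilirubin panic value and keep the two rules consistent.

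The cost is about one line of SAP wording plus the listing code. If the SAP is not reissued for this alone, the listing can be added and documented with its rationale in the CSR; SAP section 3 already calls for additional analyses to be recorded in SAP amendments and the CSR. No new data collection is needed.
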